2.2.1 Subgroups of interest

Subgroup analyses by stratification factors (Japan vs non-Japan, Gd-enhanced T1 weighted lesions 0 or ≥ 1). ([Section 2.1](#)).

Subgroup analysis by age group, weight, and gender will be included for Safety analyses as stated in the applicable sections. The subgroup categories are:

Age group (< 40, ≥ 40);

Weight (< Median, \geq Median);

Gender (Male, female).

In addition, for Cut-off 2 analysis, subgroup of home injection will be defined on basis of whether each patient had at least one home injection during the Extension part.

2.3 Patient disposition, demographics and other baseline characteristics

Patient disposition, background and demographic characteristics, and MS baseline disease characteristics will be summarized by treatment group for Cut-off 1 and final analysis based on FAS, and for Cut-off 2 analysis based on EFAS.

For final analysis, analyses will focus on patient disposition and demographics.

2.3.1 Patient disposition

The number and percentage of patients who are screened but do not enter treatment period will be presented. The summary will be on all screened patients. This summary will be included in Cut-off 1 analysis.

For Cut-off 1 analysis, the number and percentage of patients who complete the core part or prematurely discontinue study drug will be presented, along with the primary reason for discontinuation. Data collected on the end of double blind treatment period CRF page will be used to summarize this information. Similarly, the number and percentage of patients who complete the open label treatment period of the extension part or prematurely discontinue the study drug will be summarized and will be included in Cut-off 2 and final analysis.

Then number and percentage of patients who enter and complete the Safety FU period as well as the number of patients who prematurely discontinue the Safety FU period (along with the primary reason for discontinuation) will be presented. Data collected on the end of Safety FU period CRF page will be used to summarize this information. For patients who join the separate umbrella extension study an additional line will be added in the summary. The summary will be based on the patients who enter Safety FU period or the umbrella extension study and will be included in Cut-off 2 and final analysis, if needed.

The numbers of patients in each analysis set will be presented by treatment group. Protocol deviations will be summarized by deviation categories and treatment. In addition, protocol deviations that led to exclusion from the analysis set will be summarized by deviation category, deviation terms and treatment groups. Summary on protocol deviations will be based on FAS for Cut-off 1 analysis, and EFAS for Cut-off 2 or final analysis

2.3.2 Background and demographic characteristics

Demographic and background characteristics (age, gender, race, and ethnicity as collected on the Demography CRF), and prior/concomitant medications at screening visit, height, body weight, derived BMI, and employment status at baseline will be summarized by treatment group using frequency distributions (for categorical variables) and descriptive statistics of mean, standard deviation, minimum, median, and maximum (for continuous variables).

2.3.3 MS baseline disease characteristics

MS disease history, MRI baseline characteristics, and MS medication history will be summarized by treatment group.

MS disease history includes duration of MS since diagnosis (years), duration of MS since first symptom (years), number of relapses in the last 12 months prior to screening, number of relapses in the 12 to 24 months prior to screening, time since onset of most recent relapse (months) prior to screening, type of MS at study entry, and time since onset of SPMS (years).

MS baseline characteristics include EDSS, [REDACTED] and key MRI parameters (e.g., number of Gd-enhancing T1 lesions, T2 lesion volume, and normalized brain volume).

Duration of MS since diagnosis (years) will be derived as [(first dose date of the assigned treatment – MS diagnosis start date +1)/365.25]; duration of MS since first symptom (years) will be derived as [(first dose date of the assigned treatment – first MS symptom date +1)/365.25]; and time since onset of most recent relapse (months) will be derived as [(first dose date – most recent relapse onset date +1)/(365.25/12)]. In these calculations, partial dates if any will be imputed according to the rules specified in [Section 5.1](#).

MS medication history of previous disease-modifying drugs (coded by WHO drug dictionary) will be summarized by preferred term (PT) and treatment group. The number and proportion of treatment-naïve patients (i.e., patients who have not been treated with any disease-modifying drug before study enrolment) will also be presented.

2.3.4 Medical history

Medical history will be summarized by treatment group. Any condition entered on the Medical History (MH) CRF will be coded using the MedDRA dictionary. The medical history will be summarized by primary system organ class (SOC), preferred term (PT) and treatment group.

2.3.5 Smoking history and alcohol history

Data collected on smoking history and alcohol history CRF pages will be listed as appropriate.

2.4 Treatments (study treatment, rescue medication, concomitant therapies, compliance)

2.4.1 Study treatment / compliance

Analyses detailed in this section will be performed for Cut-off 1 analysis, Cut-off 2 and final analysis.

For the core part and the extension part, duration of exposure to study drug is defined as (last dose date) – (first dose date) + 31 – sum[(j+1)-th injection date – j-th injection date - 31], where j and j+1 refer to consecutive injections with injection dates more than 31 days apart (as patients are scheduled to take the subcutaneous injections every 28+/- 3 days).

Duration of exposure to study drug of core part and extension part will be summarized by treatment with number and percentage of patients and by duration category (i.e., >= 1 week, >= 2 weeks, >= 3 weeks, >= 4 weeks, >= 8 weeks, >= 12 weeks, >= 24 weeks, >= 36 weeks, >= 48 weeks, >= 60 weeks, >= 72 weeks, until end of the study). The number of patient years of exposure is calculated as (the sum of the number of days of exposure for all

patients in the group)/365.25 and will be summarized for each treatment arm, and by stratification factor Japan vs non-Japan.

Time at risk is the censoring time used for estimating exposure adjusted incidence rate of SAEs or AEs in patients who did not experience the event of interest. For patients who have experienced the event of interest, the actual date of the SAE, or AE onset will be used. Time at risk corresponds to the time window used for adverse event reporting and can serve as a denominator to certain safety analyses (e.g. in exposure-adjusted incidence rates).

Table 2-10 includes definition of time at risk for AE and SAE for Cut-off 1 analysis. It will determine the “end date of the Core part” when all randomized patients completed their assessment during the Core part.

Table 2-10 Time at risk for AE and SAE: Cut-off 1 analysis

Category	For those who completed Week 24 visit	For those discontinued the study prior to Week 24 visit
Time at risk for AE	Number of days in the study from first date of study drug to Week 24 visit date	Number of days in the study from first date of study drug to the earlier date of the following: - Safety cut-off - “End date of the Core part”*
Time at risk for SAE		Number of days in the study from first date of study drug to “end date of the Core part”

*: “End date of the Core part” will denote the date when all randomized patients complete Week 24 visit or discontinue study drug prior to Week 24 visit. This date is going to be declared by the study team, but not derived from any data.

Table 2-11 includes definition of time at risk for AE and SAE for Cut-off 2 and final analysis. It will determine the “date of Cut-off 2” when all patients entering the Extension part completed their assessment up to Week 48, or EOS visit following premature study drug discontinuation.

Table 2-11 Time at risk for AE and SAE: Cut-off 2 and final analysis

Category	Definition for Cut-off 2 analysis	Definition for final analysis
Time at risk for AE	Number of days in the study from first date of ofatumumab treatment to the earlier date of the following: - Safety cut-off - "Date of Cut-off 2"*	Number of days in the study from first date of ofatumumab treatment to safety cut-off.
Time at risk for SAE	Number of days in the study from first date of ofatumumab treatment to "date of Cut-off 2"*	Number of days in the study from first date of ofatumumab treatment to the last visit date, including Safety FU period.

*: "Date of Cut-off 2" is defined in section 2.1.1

Time-at-risk for AE and time at risk for SAE will be summarized in a similar way to exposure to investigational study medication.

Compliance to the study drug administration schedule will be calculated as duration of exposure to study drug in (days)/duration of on-treatment period in (days) * 100%. This rule means that compliance will be measured during the time interval the patient took study medication: premature discontinuation from study drug will not be considered non-compliance. Compliance to study drug administration will be summarized descriptively on SAF by treatment group. In addition, compliance will be summarized with cumulative number and percentage of patients in each compliance category (i.e., >= 20%, >= 30%, >= 40%, >= 50%, >= 60%, >= 70%, >= 80%, >= 90%, >= 95%, >= 98%, = 100%)

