5.5.4 Instructions for prescribing and taking study treatment

The study medication (ofatumumab injections or ofatumumab-matching placebo injections) will be dispensed starting at the Randomization Visit (Day 1). Drug will then be dispensed at planned visits throughout the treatment period according to [Table 6-1](#). On Day 7 and Day 14, the same time-window (+/- 1 day) as for study visit applies. Starting at Week 4, the subcutaneous injections should be administered at 4-week (28 days) intervals (+/- 3 days).

In order to assess tolerability of the initial dose of study medication (injectable), patients will be closely monitored following administration for any reactions including injection related. Patients must remain at the site under observation for a minimum of approximately **5 hours** following dosing on Day 1 and Week 24, the first dose of Double-blind treatment period in the Core part and Double-blind loading dose period of the Extension part.

From Day 1 until Week 20, patients will receive the sc injection at site. The site staff (e.g. Investigator, Study Nurse/Study Coordinator) will administer the first sc injection on Day 1. From the second sc injection (on Day 7), patients or a caregiver may inject the study medication under supervision of the study staff. Site personnel will provide training to the patients on the correct procedure for self-administration of the sc injections.

Following all assessments required for the visit of Week 24, the injection of study medication begins the Double-blind loading dose period (see [Section 5.2](#)). Patients must remain at the site under observation for a minimum of **5 hours** following dosing on Week 24.

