The **Double-blind treatment period** will start on Day 1 with randomization of the patient. Patients will be randomly assigned in a 2:1 ratio to receive either ofatumumab 20 mg sc or matching placebo sc in a double-blind fashion. Injectable study treatments (ofatumumab or

placebo) will be administered on Day 1, Day 7, Day 14, Week 4 and every 4 weeks thereafter. The Double-blind treatment period will continue until the completion of all assessments required for the Core part at Week 24.

Patients who prematurely discontinue double-blind study medication will have their end of Study (EOS) visit as soon as possible and will be followed up for safety in the Safety FU period for a minimum of 36 weeks.

The Extension part consists of 2 periods; **Double-blind loading dose period** and **Open-label treatment period**.

The **Double-blind loading dose period** will be applicable for patients who complete the Double-blind treatment period. All patients will receive ofatumumab 20 mg sc at Week 24; the Extension part starts with the injection of the Week 24. Patients randomized to ofatumumab in the Double-blind treatment period will receive the matching placebo sc at Week 25 and 26. Patients randomized to placebo in the Double-blind treatment period will receive ofatumumab 20 mg sc at Week 25 and 26. All patients will receive the study drug in a double-blind manner at Week 25 and 26.

The **Open-label treatment period** will begin at Week 28 and all patients will receive open-label ofatumumab 20 mg sc every 4 weeks in this period. This period will continue until the last patient is transferred to a planned umbrella extension study (under separate protocol requiring another informed consent).

Patients who prematurely discontinue study treatment will have their EOS visits as soon as possible and will be followed up for safety in the Safety FU period for a minimum of 36 weeks. After study drug discontinuation, during Core or Extension parts, patients may initiate alternative MS therapy according to local standard of care if clinically indicated.

The **Safety FU period** will be applicable for the following patients:

- Patients who complete this study and do not enter the planned umbrella long-term extension study
- Patients who prematurely discontinue study treatment in Core or Extension part

All Safety FU visits must be scheduled relative to the date of EOS visit.

[figure not shown]

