2.1.1 General definitions

Study drug/treatment refers to the investigational drug Ofatumumab and placebo.

“Date of Cut-off 2” is expected as the date the last patient completes all assessments at Week 48 visit. If the last patient discontinues from the study prior to Week 48 visit, “date of Cut-off 2” is the last patient's last visit.

Date of first administration of study drug/treatment, or first date of study drug/treatment, is defined depending on the analysis purposes.

- For Cut-off 1 analysis and Cut-off 2 and final *efficacy* analysis, it refers to the date when the first dose of randomized treatment is administered.
- For Cut-off 2 and final *safety* analysis, it refers to the date when the first dose of ofatumumab is administered.

Date of last administration of study drug/treatment, or last date of study drug/treatment is defined by analysis time point.

- For Cut-off 1 analysis, it refers to the date when the last dose of randomized treatment is administered up to Week 24 visit.
- For Cut-off 2 analysis, it refers to the date when the last dose of treatment is administered up to the date of Cut-off 2.
- For final analysis, it refers to the date when the last dose of treatment is administered up to EOS visit.

Study day is defined as: if after first date of study drug, then (Study Day) = (Date) – (first date of study drug) +1; if before first date of study drug, then (Study Day) = (Date) – (first date of study drug); Study Day 1 is defined as the date of the first administration of study drug; there is no Study Day 0.

Duration of an event is calculated as (event end date) – (event start date) +1.

1 month is counted as 30 days unless otherwise specified.

Baseline is defined for each cut-off analysis.

- For Cut-off 1 analysis, and Cut-off 2 and final *efficacy* analysis, baseline is defined as the last non-missing result before or on the first date of study drug.
- For Cut-off 2 and final *safety* analysis, definition of baseline depends on each patient's treatment course in the study
 - For a patient continuously having ofatumumab across Core and Extension parts, baseline is defined as the last non-missing result before or on the first date of study drug.
 - For a patient switching the treatment from placebo to ofatumumab when entering the Extension part, baseline is defined as the dose date of ofatumumab at Week 24. *For analysis on vital signs*, the baseline is defined as *the pre-dose measurement* at Week 24.

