2.1.4 Treatment group for Cut-off 2 and final analysis

For analysis based on Extension FAS, the following treatment groups will be displayed:

- OMB 20mg: This will include patients randomized to ofatumumab treatment group and having at least one dose of ofatumumab in Extension part.
- Placebo – OMB 20mg: This will include patients randomized to placebo treatment group, and having at least one dose of ofatumumab in Extension part.

For safety analysis based on Extension SAF, the following treatment groups will be displayed:

- OMB 20mg: This will include patients treated with ofatumumab during Core part and having at least one dose of ofatumumab in Extension part.
- Placebo – OMB 20mg: This will include patients treated with placebo during Core part, and having at least one dose of ofatumumab in Extension part. For these patients, analysis will include only assessments on or after treatment at Week 24, and Safety FU period if necessary.

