2.8 Safety analyses

Safety analyses during the study will be detailed below. All safety analyses will be based on the SAF for Cut-off 1 analysis and ESAF for Cut-off 2 and final analysis, unless explicitly stated otherwise.

Patients will be grouped by the actual treatment received. Safety data for the core part will be reported for the first time when the double-blind loading dose period has been completed by the last patient (Cut-off 1 analysis). Safety data for the extension part including Safety FU period

data will be reported for the first time when the last patient has finished 48 weeks of treatment (Cut-off 2 analysis). Safety data beyond the cut-off 2 will be reported separately.

Unless explicitly otherwise stated, for patients who entered Safety FU period, safety data will be reported up to and including the safety cut-off.

- For Cut-off 1 analysis, safety data reported up to safety cut-off, the latest visit date including Safety FU, or Week 24 visit date, whichever comes first.
- For Cut-off 2 and final analysis, safety data reported up to safety cut-off or the latest visit date including Safety FU, whichever comes first.

The assessment of safety will be primarily based on the frequency of adverse events (including death and non-fatal serious adverse events). Additional safety assessments include laboratory tests, physical examination (including examination of skin), vital sign measures, ECG evaluations and assessment of suicidality. Clinically significant findings in these additional safety assessments will be reported as adverse events and analyzed as such. In addition, all safety assessments will be summarized or listed as appropriate.

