2.8.1 Adverse events (AEs)

Treatment emergent adverse events (TEAE) is defined as any adverse event which start on or after the day of the first dose of study drug.

TEAEs will be reported if their onset days are no greater than “time at risk for AE”. Similarly, serious TEAEs will be reported if their onset days are no greater than “time at risk for SAE”.

TEAE will be coded by primary system organ class and preferred term according to the Medical Dictionary for Regulatory Activities (MedDRA). The MedDRA version used for reporting the study will be described in a footnote.

Incidence of TEAEs will be summarized (number and percentage of patients reporting any TEAE by primary SOC, preferred term, and treatment group. Serious TEAEs, drug related TEAEs, TEAEs leading to premature discontinuation from study drug, TEAE leading to study drug interruption, and most common TEAEs ($\geq 5\%$ in any of the treatment groups) will be presented in a similar format as adverse events. In addition, incidence of TEAEs will be summarized by SOC, preferred term, and maximum CTCAE grade. Missing CTCAE grade will not be imputed. The CTCAE version 5.0 will be used.

For Cut-off 1 analysis, odds ratios (investigational drug vs. control) with 95% confidence intervals will be presented along with the summary of any TEAEs and the summary of serious TEAEs. Details in calculations of odds ratios and their 95% confidence intervals are provided in Section 5.7.1. Incidence of any TEAEs will be plotted by SOC, along with the odds ratio (and corresponding 95% confidence interval) for TEAEs in each SOC. Odds ratios provide appropriate inferences for events that are likely to occur at certain times (e.g., injection related reactions) while no constant risk over time is expected.

If a patient reports more than one adverse event within the same primary SOC, the patient will be counted only once with the maximum CTCAE grade at the SOC level, where applicable.

All AEs will be presented in listings.

The following summaries will be repeated for Cut-off 2 and final analysis:

- Overall TEAE
- TEAE by CTCAE grade
- Serious TEAE
- Drug-related TEAE
- TEAE causing study drug discontinuation
- TEAE leading to study drug interruption
- Serious TEAE causing study drug discontinuation
- Most common TEAE
- Infections and infestations TEAE

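### Core AE counting for Week 24 completers stops by calendar date rather than at the Week 24 injection, so on the inclusive day count same-day reactions to placebo patients' first ofatumumab dose count under placebo

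*SAP*

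**What the plan says.** SAP 2.4.1, Table 2-10, defines Cut-off 1 time at risk for AEs in patients who complete Week 24 as "Number of days in the study from first date of study drug to Week 24 visit date". The end point is a date, with no time of day and no pre-dose limit. SAP 2.8.1 then makes this the counting rule: "TEAEs will be reported if their onset days are no greater than" the time at risk for AE. SAP 2.8 gives the same limit for Cut-off 1 in general: "safety data reported up to safety cut-off, the latest visit date including Safety FU, or Week 24 visit date, whichever comes first".

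On how days are counted, SAP 2.1.1 has, for dates after the first dose, "then (Study Day) = (Date) – (first date of study drug) +1". SAP 5.7.2 adds 1 in the same way for event times in the incidence rates. Table 2-10 does not say whether 1 is added.

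The boundary between the parts is placed at the injection. SAP 1.1: "All patients will receive ofatumumab 20 mg sc at Week 24; the Extension part starts with the injection of the Week 24". Protocol 5.5.4: "Following all assessments required for the visit of Week 24, the injection of study medication begins the Double-blind loading dose period".

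For Cut-off 2, SAP 2.1.4 says that for patients who switched from placebo, "analysis will include only assessments on or after treatment at Week 24". The TEAE definition in SAP 2.8.1, however, works by day: "any adverse event which start on or after the day of the first dose of study drug".

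**The concern.** The AE window closes at the end of a calendar date, but the change of drug happens part-way through that date. For placebo patients the Week 24 injection is the first exposure to ofatumumab. Protocol 1.1 reports that in the earlier subcutaneous study injection-related reactions came mainly after the first dose. These are the events most likely to start within hours of that injection, while the patient is under the observation of at least 5 hours that Protocol 5.5.4 requires.

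Cut-off 1 safety tables group patients by treatment received, and no Cut-off 1 rule moves a placebo patient's post-injection AE out of the placebo column. SAP 2.8.1.1.1 puts injection-site and systemic reactions into the general AE tables as preferred terms, and SAP 2.8.1 names injection reactions as a reason for using odds ratios. Active-drug reactions would therefore raise placebo incidence and understate the drug's excess in the very comparison chosen to show it. The Cut-off 1 analysis is meant to support registration in Japan.

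A related inconsistency arises at Cut-off 2, where a switcher's TEAEs begin on the day of the first ofatumumab dose. On the inclusive reading, one same-day AE can count under placebo at Cut-off 1 and under ofatumumab at Cut-off 2.

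**Working it through.** The plan states no figure for this rule, so there is none to reproduce. The check applies the rule to one patient and then illustrates its size.

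**Day count.** Take a placebo patient whose Week 24 visit and injection fall on the target day, 167 days after the first dose.

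- Onset day of an AE starting on that date (SAP 2.1.1): 167 + 1 = 168.
- Inclusive time at risk: 167 + 1 = 168. Since 168 ≤ 168, the AE is counted under placebo, whether it starts before or after the injection.
- Plain subtraction: time at risk is 167. Since 168 > 167, the AE is not counted, and neither is a genuine Core AE that began that morning before the injection.

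Neither reading gives the stated boundary. The inclusive one fits better with SAP 2.1.1, SAP 5.7.2 and the limit in SAP 2.8, which reports data up to the visit date.

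**Inputs for size.** Planned allocation is 60 patients at 2:1, so 40 ofatumumab and 20 placebo. The dropout allowance is 10%, so 90% of placebo patients are taken to reach the Week 24 injection. Starting reaction rates of 52% and 15% come from the earlier subcutaneous study (Protocol 1.1). The same-day reaction rate f after the first active dose is not given and is assumed to be 5%, 10% or 20%.

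Odds ratio without the Week 24 day: (0.52/0.48) / (0.15/0.85) = 6.14.

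Placebo incidence with that day included: 0.15 + 0.85 × 0.90 × f. Expected extra placebo cases: 20 × 0.85 × 0.90 × f. Of 20 placebo patients, 17 are reaction-free before Week 24, and 17 × 0.90 is about 15. The chance of at least one misattributed case is then 1 − (1 − f)^15. The chance of at least two is that value minus 15 × f × (1 − f)^14.

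| f | Placebo incidence | Odds ratio | Expected extra cases | P(≥1) | P(≥2) |
|---|---|---|---|---|---|
| 5% | 0.188 | 4.67 | 0.77 | 0.537 | 0.171 |
| 10% | 0.227 | 3.70 | 1.53 | 0.794 | 0.451 |
| 20% | 0.303 | 2.49 | 3.06 | 0.965 | 0.833 |

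**In whole patients**, with 21 of 40 on ofatumumab and the conditional exact interval that SAP 5.7.1 specifies:

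| Placebo cases of 20 | Odds ratio | Exact 95% CI |
|---|---|---|
| 3 | 6.26 | 1.43 to 37.4 |
| 4 | 4.42 | 1.12 to 20.9 |
| 5 | 3.32 | 0.90 to 13.7 |

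Two misattributed cases would be enough to take the interval across 1 in this example.

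**The case against.** The strongest reply is that this is an ambiguity, not a demonstrated misattribution. Table 2-10 does not write +1 where other SAP formulas do, and on plain subtraction the bias disappears. The intent is also clear: Cut-off 1 is described as Core data, the Extension starts with the injection, and SAP 2.1.4 gives switchers' assessments from that treatment onwards to ofatumumab. It is true that +1 is inferred for Table 2-10. But plain subtraction fits the rest of the SAP poorly and loses real Core AEs, so the boundary is missed on either reading, and a clear intent does not change a counting rule that contradicts it.

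Second, SAP 2.8.1.1.1 already compares reaction and injection times, summarises reactions by injection and lists each with its time to onset, so a reader would see the Week 24 reactions for what they are. That stands, and it limits the harm. It does not correct the overall TEAE and odds-ratio rows.

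Third, the size is assumed. This also stands. The 52% and 15% rates come from other dose regimens and any onset time, and f is in neither document. The steroid premedication recommended at Week 24 may lower f. Site and systemic reactions are separate preferred terms, so no preferred-term row carries the combined odds ratio. The exact intervals overlap heavily.

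Fourth, appearing in both cut-offs is not in itself a fault, because the analyses are separate and AE odds ratios are planned only for Cut-off 1. That is fair. The fault is that the same event would be attributed to different treatments in the two.

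**Conclusion.** The concern holds. Table 2-10 with SAP 2.8 and 2.8.1 ends completers' Core AE counting by date, while both documents place the end of the Core part at the injection given later that day. On the natural, inclusive reading, same-day reactions to placebo patients' first ofatumumab dose are counted under placebo, and Core AE odds ratios are biased towards 1.

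The severity is minor. Only onsets on the Week 24 date are affected, mainly injection reactions; a reaction starting the next day falls outside the window. No success criterion rests on the AE odds ratios, and no effect on efficacy, or material effect on SAEs, is shown. Under the illustrative rates, one or two misattributed placebo cases are plausible, enough to lower an odds ratio of about 6 to between 3 and 4.5. The conclusion about the rule assumes that +1 applies to Table 2-10 and that visit and injection share a date, as Protocol 5.5.4 implies. The size depends wholly on the assumed f.

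**What to change.** In Table 2-10, SAP 2.8 and SAP 2.8.1:

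- End Core AE counting for completers at the Week 24 injection, or at the Week 24 visit date (inclusive) if no injection is given.
- Assign Week 24 injection-reaction records to the Extension by their recorded times.
- State one convention for same-day AEs without a time.
- State in Table 2-10 whether +1 applies.
- Align the day-level TEAE start rule in SAP 2.8.1 with SAP 2.1.4, so that a switcher's AE on that date counts in one period only.

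The cost is two or three sentences and a date/time comparison that SAP 2.8.1.1.1 already makes for reactions. Neither document says that onset times are collected for other AEs, so a few same-day events would be allocated by convention and may land in the wrong period. This SAP version is dated September 2020, after the Week 48 amendment, so Core tables may already exist. If so, the change means a rerun or a footnote to the affected rows, identified as made after the Core analysis.
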